12.1 Definitions

Adverse event

An adverse event (AE) is any untoward medical occurrence in a subject administered a product, and which does not necessarily have a causal relationship with this treatment.

An AE can therefore be any unfavourable and unintended sign (including an abnormal laboratory finding), symptom or disease temporally associated with the use of a product, whether or not considered related to the product.

An AE includes:

- A clinically significant worsening of a concomitant illness.
- A clinical laboratory adverse event (CLAE): a clinical laboratory abnormality which is clinically significant, i.e. an abnormality that suggests a disease and/or organ toxicity and is of a severity that requires active management. Active management includes active treatment or further investigations, for example change of medicine dose or more frequent follow-up due to the abnormality.

The following should **not** be reported as AEs:

- Pre-existing conditions, including those found as a result of screening procedures (preexisting conditions should be reported as medical history or concomitant illness).
- Pre-planned procedures unless the condition for which the procedure was planned has worsened from the first trial related activity after the subject has signed the informed consent.
- Non-serious hypoglycaemia is an AE, but is reported on a hypoglycaemic episode form instead of on an AE form, see section 8.3.3.

The following three definitions are used when assessing an AE:

- Severity
- Mild no or transient symptoms, no interference with the subject's daily activities.
- Moderate marked symptoms, moderate interference with the subject's daily activities.
- Severe considerable interference with the subject's daily activities; unacceptable.

CONFIDENTIAL

Date:

Version:

Status:

Page:

04 September 2015 Novo Nordisk 1.0 Final 33 of 67

• Causality

Relationship between an AE and the relevant trial product(s):

- **Probable** Good reason and sufficient documentation to assume a causal relationship.
- **Possible** A causal relationship is conceivable and cannot be dismissed.
- Unlikely The event is most likely related to aetiology other than the trial product.

• Final outcome

- Recovered/resolved The subject has fully recovered, or by medical or surgical treatment the condition has returned to the level observed at the first trial-related activity after the subject signed the informed consent.
- Recovering/resolving The condition is improving and the subject is expected to recover from the event. This term is only applicable if the subject has completed the trial or has died from another AE.
- Recovered/resolved with sequelae The subject has recovered from the condition, but with lasting effect due to a disease, injury, treatment or procedure. If a sequelae meets an SAE criterion, the AE must be reported as an SAE.
- Not recovered/not resolved The condition of the subject has not improved and the symptoms are unchanged, or the outcome is not known.
- Fatal This term is only applicable if the subject died from a condition related to the reported AE. Outcomes of other reported AEs in a subject before he/she died should be assessed as "recovered/resolved", "recovering/resolving", "recovered/resolved with sequelae" or "not recovered/not resolved". An AE with fatal outcome must be reported as an SAE.
- Unknown This term is only applicable if the subject is lost to follow-up.

Serious adverse event

A serious adverse event (SAE) is an experience that at any dose results in any of the following:

- Death.
- A life-threatening^a experience.
- In-patient hospitalisation^b or prolongation of existing hospitalisation.
- A persistent or significant disability or incapacity^c.
- A congenital anomaly or birth defect.
- Important medical events that may not result in death, be life threatening^a or require hospitalisation^b may be considered an SAE when based on appropriate medical judgement they may jeopardise the subject and may require medical or surgical intervention to prevent one of the outcomes listed in the definition of SAE^d.

Suspicion of transmission of infectious agents via the trial product must always be considered an SAE.

Protocol		Date:	04 September 2015	Novo Nordisk
Trial ID: NN2211-4232	CONFIDENTIAL	Version:	1.0	
UTN: U1111-1170-7035		Status:	Final	
EudraCT no.: 2015-002417-29		Page:	34 of 67	

- ^a. The term "life threatening" in the definition of SAE refers to an event in which the subject was at risk of death at the time of the event. It does not refer to an event which hypothetically might have caused death if it was more severe.
- ^b. The term "hospitalisation" is used when a subject:
 - Is admitted to a hospital or in-patient, irrespective of the duration of physical stay, or
 - Stays at the hospital for treatment or observation for more than 24 hours

Medical judgement must always be exercised, and when in doubt, the hospital contact should be regarded as a hospitalisation. Hospitalisations for administrative, trial related and social purposes do not constitute AEs and should therefore not be reported as AEs or SAEs. Hospital admissions for surgical procedures, planned before trial inclusion, are not considered AEs or SAEs.

- ^c. A substantial disruption of a subject's ability to conduct normal life functions (e.g. following the event or clinical investigation the subject has significant, persistent or permanent change, impairment, damage or disruption in his/her body function or structure, physical activity and/or quality of life).
- ^d. For example intensive treatment in an emergency room or at home of allergic bronchospasm, blood dyscrasias or convulsions that do not result in hospitalisation, or development of drug dependency or drug abuse.

Non-serious adverse event

A non-serious AE is any AE which does not fulfil the definition of an SAE.

Medical event of special interest

A medical event of special interest (MESI) is an event which, in the evaluation of safety, has a special focus. A MESI is an AE (SAE or non-serious AE) which fulfils one or more of the below defined MESI criteria.

Medication errors concerning trial products:

- Administration of wrong drug.
- Wrong route of administration, such as intramuscular instead of subcutaneous.
- Administration of an overdose with the intention to cause harm (e.g. suicide attempt).
- Accidental administration of a lower or higher dose than intended, however the administered dose must deviate from the intended dose to an extent where clinical consequences for the trial subject were likely to happen as judged by the investigator, although they did not necessarily occur.

Protocol		Date:	04 September 2015	Novo Nordisk
Trial ID: NN2211-4232	CONFIDENTIAL	Version:	1.0	
UTN: U1111-1170-7035	CONFIDENTIAL	Status:	Final	
EudraCT no.: 2015-002417-29		Page:	35 of 67	

Technical complaint

A technical complaint is any written, electronic, or oral communication that alleges product (medicine or device) defects. The technical complaint may be associated with an AE, but does not concern the AE itself.

Examples of technical complaints:

- The physical or chemical appearance of trial products (e.g. discoloration, particles or contamination)
- The packaging material (e.g. leakage, cracks, rubber membrane issues or errors in labelling text)
- Problems related to devices (e.g. to the injection mechanism, dose setting mechanism, push button or interface between the pen and the needle)

ProtocolDate:Trial ID: NN2211-4232CONFIDENTIALVersioUTN: U1111-1170-7035EudraCT no.: 2015-002417-29Page:	04 September 2015 Nov n: 1.0 Final 36 of 67	ovo Nordisk
----------------------------------------------------------------------------------------------------------	-------------------------------------------------------------	-------------

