4.2.2 Secondary endpoints

4.2.2.1 Supportive secondary endpoints

- Time to premature treatment discontinuation (for any reason including inadequate glycaemic control)
- Change from baseline in HbA_{1c} at 104 weeks or at premature treatment discontinuation
- Number of subjects who at 104 weeks or at premature treatment discontinuation achieve (Yes/No):
 - \circ HbA_{1c} \leq 6.5% (48 mmol/mol) *
 - \circ HbA_{1c} \leq 7.0% (53 mmol/mol) without weight gain *
 - \circ HbA_{1c} \leq 7.0% (53 mmol/mol) without treatment emergent severe hypoglycaemic episodes or blood glucose confirmed symptomatic hypoglycaemic episodes
 - \circ HbA_{1c} \leq 7.0% (53 mmol/mol) without weight gain and no treatment emergent severe hypoglycaemic episodes or blood glucose confirmed symptomatic hypoglycaemic episodes
- Change from baseline at 104 weeks or at premature treatment discontinuation will be evaluated for:
 - Fasting plasma glucose (FPG) *
 - Body weight *
 - o BMI
 - Systolic and diastolic blood pressure
- Number of severe hypoglycaemic episodes
- Number of severe or blood glucose confirmed symptomatic hypoglycaemic episodes
- Number of documented symptomatic hypoglycaemic episodes (ADA)
- Number of serious adverse events (SAEs)
- Number of AEs leading to permanent discontinuation of trial product
- Change from baseline at 104 weeks or at premature treatment discontinuation will be evaluated for:
 - o Lipids
 - o Biochemistry
 - Haematology
 - o Pulse

* Key supportive secondary endpoint prospectively selected for disclosure (e.g. clinicaltrials.gov and EudraCT)

CONFIDENTIAL

Date: Version: Status: Page:

5 Trial design

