8.1.5 Withdrawals

If a subject is withdrawn from the trial, the investigator must aim to undertake procedures similar to those for visit 12 as soon as possible if acceptable to the subject. The end-of-trial form must be completed, and final drug accountability must be performed even if the subject is not able to come to the trial site. In addition the follow-up telephone contact (visit 13) should be completed approximately 1 week after the early treatment discontinuation visit if possible. After that the case book must be signed.

Although a subject is not obliged to give his/her reason(s) for withdrawing from a trial, the investigator must make a reasonable effort to ascertain the reason(s), while fully respecting the subject's rights. Where the reasons are obtained, the primary reason for not completing the trial must be specified on the end-of-trial form in the eCRF.

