- Factors contributing to the episode (i.e. physical activity, missed meal, diet changed, medication error (i.e. overdose, mix-up between products), other factors not listed, please specify or none)
- Did the subject experience seizure?
- Was the subject unconscious/comatose?
- Did the subject experience any of the following symptoms?
- Autonomic: sweating, trembling, hunger or palpitations
- Neuroglycopenic: confusion, drowsiness, speech difficulty, visual disturbances, odd behaviour, impaired balance or incoordination
- General malaise: headache or malaise
- Did the subject experience other symptoms? Please specify
- Description of the episode, if applicable

A hypoglycaemic episode form must be filled in for each hypoglycaemic episode. If the hypoglycaemic episode fulfils the criteria for an SAE then an AE form and a safety information form must also be filled in, see section $\underline{12}$.

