12.2 Reporting of adverse events

All events meeting the definition of an SAE (see section 12.1), MESI (see section 12.1), AEs leading to permanent discontinuation of trial product and pregnancies (see section 12.5) must be collected and reported. This includes events from first trial related activity after the subject has signed the informed consent until the end of trial (visit 13). The events must be recorded in the applicable eCRF forms in a timely manner, see timelines below and Figure 12–1.

During each contact with the investigator, the subject must be asked about AEs, for example by asking: "Have you experienced any problems since the last contact?" AEs are either observed by the investigator or reported by the subject.

The investigator will evaluate the need for reporting of AEs. The investigator must report the following AEs in the eCRF:

- All SAEs
- AEs leading to permanent discontinuation of investigational product
- MESIs

The investigator should report the diagnosis, if available. If no diagnosis is available, the investigator should record each sign as individual AEs using separate AE forms. The investigator must evaluate the severity and causality for each event.

For SAEs that could have resulted from hypoglycaemia (for example sudden death, seizure, trauma, fractures, fall, motor vehicle accident etc), the narrative should include information whether hypoglycaemia could have contributed to these events.

- The investigator must enter the AE in the eCRF and tick the seriousness box within 24 hours of obtaining knowledge of the SAE
- The safety information form must be completed within 5 days of obtaining knowledge of the SAE

If for some reason the eCRF is unavailable, the AE information should be reported to Novo Nordisk by fax, telephone, e-mail or courier within the same timelines.

Contact details (fax, telephone, e-mail and address) are provided to each site.

All SAEs, MESIs and AEs leading to permanent treatment discontinuation observed either by the investigator or the subject, must be reported by the investigator and evaluated. Novo Nordisk assessment of expectedness is performed according to the following reference documents:

- Company core data sheet (CCDS), Victoza[®], 6.0 mg/mL, version 17.0 or any updates thereto
- Non Novo Nordisk A/S marketed products: European summary of product characteristics or other relevant labelling, current version or any updates thereto.

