Protocol	NTIAL Date:	04 September 2015
Trial ID: NN2211-4232	Version:	1.0
UTN: U1111-1170-7035	Status:	Final
EudraCT no.: 2015-002417-29	Page:	37 of 67

All SAEs, MESIs, AEs leading to permanent treatment discontinuation and AEs in connection with pregnancies must be recorded by the investigator on an AE form. The investigator should report the diagnosis, if available. If no diagnosis is available, the investigator should record each sign and symptom as individual AEs using separate AE forms.

For SAEs, a safety information form must be completed in addition to the AE form. If several symptoms or diagnoses occur as part of the same clinical picture, one safety information form can be used to describe all the SAEs.

MESIs, regardless of seriousness, must be reported using both AE form, safety information form and a medication error form. The medication error form is a form tailored to collect specific information related to the individual MESI. The AE form for a non-serious AE not fulfilling the MESI criteria should be signed when the event is resolved or at the end of the trial.

[figure not shown]
Timelines for initial reporting of AEs:

The investigator must complete the following forms in the eCRF within the specified timelines:

- **SAEs**: The AE form **within 24 hours** and the safety information form **within 5 calendar** days of the investigator's first knowledge of the SAE. Both forms must be signed within 7 calendar days from the date the information was entered in the eCRF.
- SAEs fulfilling the MESI criteria: In addition to above, the medication error form within 14 calendar days of the investigator's first knowledge of the AE.
- Non-serious AE fulfilling the MESI criteria: The AE form, safety information form and medication error form within 14 calendar days of the investigator's first knowledge of the event.

If the eCRF is unavailable, the concerned AE information must be reported on paper forms and sent to Novo Nordisk by fax, e-mail or courier within the same timelines as stated above. When the eCRF becomes available again, the investigator must enter the information on the appropriate forms in the eCRF.

Contact details (fax, telephone, e-mail and address) are provided in the investigator trial master file.

All timelines are from the investigator's first knowledge of the event

Figure 12–1 Initial reporting of AEs

Reporting of trial product-related SUSARs by Novo Nordisk:

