5.2.3 ADAE – Adverse events analysis

ADAE contains all reported events for randomised subjects. All events from the first trial-related activity after the subject has signed the informed consent until the end of the post-treatment follow-up period are included. Data is built on SDTM data AE, SUPPAE, RELREC, and information from ADSL.

CONFIDENTIAL

Date: Version: Status: Page:

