5.2.8 ADHYPO – Hypoglycaemic episode analysis

The ADHYPO contains data on all reported hypoglycaemic episodes for randomised subjects. All events from the first trial-related activity after the subject has signed the informed consent until the end of the post-treatment follow-up period are included. Data is built on SDTM data XH, SUPPXH, RELREC, and information from ADSL.

The ONTRTFL defines the on-treatment period for hypoglycaemic episodes as described in section 2.3.3. The TRTEMFL defined the on-treatment period with an addition of 1 more day (section 3.6.5).

The variables ACAT1 contains the analysis category 1 of ADA hypoglycaemic classification described in protocol. Each of the ADA classification categories are also marked in the variable flags ADASYMFL, ADDOCSFL, ADPROBFL, ADPSEUFL, ADSEVFL, ADUNCLFL, ADUNNSFL.

The variables ACAT2 contains the analysis category 1 of NN hypoglycaemic classification described in protocol. Each of the NN classification categories and merged categories are also marked in the variable flags NNASCOFL, NNCONFL, NNSECOFL, NNSEVFL, NNSYCOFL, NNSYSEFL, NNUNCLFL.

The date-time imputations follow the derivation rules in 3.6.1, and note that missing time information imputed to 00:00 implies that the hypoglycaemic episodes are imputed to occur during day-time.

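### Protocol sections 12.1 and 8.3.3 conflict with 12.2 on whether non-serious hypoglycaemia that ends treatment needs an AE form, so the discontinuation endpoint can miss such events

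*Protocol*

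**What the plan says.** Protocol section 12.1 puts non-serious hypoglycaemia in its list of things not to be reported as AEs, while accepting that it is one: "Non-serious hypoglycaemia is an AE, but is reported on a hypoglycaemic episode form instead of on an AE form". It refers the reader to section 8.3.3. That section requires a hypoglycaemia form for each episode and names one condition for an additional AE form: "If the hypoglycaemic episode fulfils the criteria for an SAE then an AE form and a safety information form must also be filled in".

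Section 12.2 starts from the consequence of the event. Its list of what the investigator must report includes "AEs leading to permanent discontinuation of investigational product", and its rule on forms is that "AEs leading to permanent treatment discontinuation and AEs in connection with pregnancies must be recorded by the investigator on an AE form". Hypoglycaemia is not excepted.

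Section 4.2.2.1 makes "Number of AEs leading to permanent discontinuation of trial product" a supportive secondary endpoint, and section 17.4.1.2 places it among the safety endpoints.

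In the SAP, section 5.2.3 says of ADAE: "Data is built on SDTM data AE, SUPPAE, RELREC, and information from ADSL". Section 5.2.8 says of ADHYPO: "Data is built on SDTM data XH, SUPPXH, RELREC, and information from ADSL".

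**The concern.** A non-serious hypoglycaemic episode that causes a subject to stop trial product for good falls under both sets of instructions, and they give opposite answers on the AE form. Staff handling such an episode are likely to look first at the two hypoglycaemia-specific passages, and neither mentions discontinuation.

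The endpoint is exposed because AE collection is reduced in this trial. Section 12.2 asks for SAEs, medical events of special interest (medication errors), AEs leading to discontinuation, and pregnancy-related events. For an ordinary non-serious event, having led to discontinuation is what earns it an AE form. If sites resolve the conflict differently, the count depends partly on which section each site read. That weakens a pre-specified safety comparison in an open-label trial.

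**Working it through.** The documents contain no figure for this point, so the check is a comparison of texts followed by tracing the data.

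**1. The three form rules, applied to a non-serious episode that ends treatment**

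| Protocol section | Trigger for an AE form | Result for this case |
|---|---|---|
| 12.1 | None for non-serious hypoglycaemia | No AE form |
| 8.3.3 | Episode is an SAE | No AE form |
| 12.2 | AE led to permanent discontinuation | AE form required |

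Because 12.1 itself classes the episode as an AE, it is within the scope of 12.2. No order of precedence is stated.

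**2. Comparison with neighbouring sections.** For worsening of a concomitant illness, section 8.2.1 names two triggers for AE reporting: SAE criteria, or permanent treatment discontinuation. Section 8.2.2 uses the same pair for recording concomitant medication. Section 8.3.3 names only the first. Amendment 1 changes other text in 8.2.1 and updates Figure 12–1, but lists no change to 8.3.3 or to the text of 12.1. This pattern suggests an omission rather than a deliberate exclusion.

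**3. What the hypoglycaemia record holds.** The items listed in 8.3.3 cover timing, glucose value, symptoms, last dose, last meal, assistance and contributing factors. None asks whether trial product was stopped.

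**4. Route to the endpoint.** ADAE takes its events from the AE domain and ADHYPO from XH. Both draw on RELREC, but a link between records cannot supply an AE record that was never made. The SAP describes no rule that counts XH episodes in the discontinuation endpoint. An episode recorded only on the hypoglycaemia form therefore has no described route into the count.

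**5. Other capture.** Under section 8.1.5, where a reason for withdrawal is obtained, "the primary reason for not completing the trial must be specified on the end-of-trial form in the eCRF". Nothing in the SAP feeds that reason into this endpoint.

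**6. Scale, by assumption only.** Section 17.1 plans for 20% premature discontinuation without inadequate glycaemic control in each arm. With 1994 / 2 = 997 per arm, 0.20 × 997 = 199.4, which agrees with the 200 per arm in Amendment 1. Let s be the share of these caused by non-serious hypoglycaemia, and f the fraction handled under 12.1 rather than 12.2. The number missed per arm is 200 × s × f. Neither s nor f is in the documents. With f = 1, the upper limit:

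- s = 0%: 0
- s = 1%: 200 × 0.01 = 2
- s = 5%: 200 × 0.05 = 10
- s = 10%: 200 × 0.10 = 20

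With f = 0, where every site applies 12.2, the number is 0 whatever s is.

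**The case against.** The strongest reply is that 12.2 already settles the matter. It is mandatory, it makes no exception, and 12.1 concedes that the episode is an AE. Section 12.3 also has a follow-up rule for non-serious AEs leading to discontinuation. A site reading all of section 12 would file the form, and the event would reach ADAE. This stands against any claim that such events are certainly lost. It does not remove the conflict, because 12.1 is equally explicit in the other direction.

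Second, the consequence is limited. Section 17.4.1.2 plans a descriptive display of AEs, with no between-arm test. Time to premature treatment discontinuation for any reason is tested separately and counts every stop. Hypoglycaemic episodes have three endpoints of their own, analysed by negative binomial regression. All of this stands. However, neither of those analyses shows how many subjects stopped because of an adverse event, which is what this endpoint is for.

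Third, some sources are not available: Figure 12–1 and its update, the eCRF, the project-level programming specification and the table shells. Any of them might settle the routing, and the field list in 8.3.3 need not be the complete eCRF form. This is a fair limit on how firmly the data gap can be asserted.

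A reader might go further and infer that the loss falls mainly in the OAD arm, because sulphonylureas and meglitinides are allowed there, and that the comparison is therefore biased against Victoza. The documents do not support this. They give no hypoglycaemia rates by arm or by OAD class and no reasons for stopping. Section 5.4 leaves the choice among six classes to the investigator without stating an expected mix, and planned non-glycaemic discontinuation is the same in both arms.

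**Conclusion.** The protocol contradicts itself on one defined case: non-serious hypoglycaemia that leads to permanent discontinuation of trial product. Such events can be missed by the supportive safety endpoint, to the extent that sites followed 12.1 and 8.3.3 instead of 12.2. They are not certain to be missed. Confidence is high for the conflict in the text and low for its effect on the count. The scale of 0 to 20 per arm rests entirely on an assumed share of 0% to 10% and on the worst case for site practice; any split between arms would be a further assumption. The HbA1c-based primary endpoint and the sample size are not affected. The point merits correction because a pre-specified safety count should not depend on which section a site consulted.

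**What to change.** Amend sections 12.1 and 8.3.3 to match 12.2 and the two-trigger pattern in 8.2.1: a hypoglycaemic episode that is serious, or that leads to permanent discontinuation of trial product, gets an AE form in addition to the hypoglycaemia form. Check that Figure 12–1 and the eCRF instructions say the same.

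For data already collected, cross-check three sources before the endpoint is counted: ADAE, the hypoglycaemia records, and the end-of-trial reasons for not completing. Query each subject whose hypoglycaemia record or end-of-trial reason points to a stop because of hypoglycaemia but who has no matching AE record. The end-of-trial form should prompt queries and not serve as a source of counted events, because its reason categories are not shown and a reason is recorded only where one was obtained.

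The cost is one clause in each of two protocol sections, a few more AE forms, and one reconciliation listing with its queries.
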